6.8 Statistics

A Geisinger statistician will complete the statistics. All statistical analyses will be performed with SAS (SAS 9.4, SAS Institute, Cary, NC), Stata (SE 14.2, StataCorp, LLC, College Station, TX), or R (R 3.5.2, The R Foundation, Vienna, Austria) statistical software, with p-values of <0.05 considered statistically significant.

6.8.1 Statistical Analysis Plan

We will calculate frequencies for categorical data and means with standard deviations for continuous variables. Bivariate comparisons will be explored using Chi-square or Fisher's exact test for categorical variables and two-sample t-tests or Mann-Whitney tests for continuous variables.

Because pain is expected to decrease over time, and because pain scores may vary by day and time of day administered, we will plan to plot NPRS score vs. time for every patient over the 8-week treatment period, using straight-line interpolation between measurements, which will allow us to use all available measurements (even if some patients recorded more NPRS scores than others) and will avoid placing too much emphasis on a measurement at a single time point (e.g. the 21-day measurement). We will compute a percent-area-under-the-curve (NPRS-%AUC)

measurement where 100% would indicate pain scores of 10 across the entire time period. Each patient will have a different NPRS-%AUC, forming a distribution of measures in each of the two groups, and we will use an unpaired t-test to compare the mean NPRS-%AUC for patients before and after the intervention.

Percent change in PSEQ-2, PCS-4, CPAQ-8, ODI, SF-12 and total opioid usage (measured in MME) will be compared between groups using ANOVA, or, if more appropriate, a nonparametric Kruskal-Wallis test.

Covariates in the analysis of covariance models include study site, sex, duration of pain, opioid use, and baseline outcome scores.

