6.6 Primary Endpoints

Primary endpoints include 1) the percent change from baseline (defined as the average of the 5-7 pain scores obtained in the week prior to enrollment/randomization) in the average daily low back NPRS score during weeks 1-4 and weeks 1-8. The primary analysis will compare the EaseVR group against the VR sham group.

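### The only NPRS test in section 6.8.1 contradicts itself and does not analyse the primary endpoint defined in section 6.6

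*Combined protocol and SAP*

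**What the plan says.** Section 6.6 fixes the primary endpoint. The measure is "the percent change from baseline (defined as the average of the 5-7 pain scores obtained in the week prior to enrollment/randomization"), applied to average daily low back NPRS in two windows, weeks 1-4 and weeks 1-8. The comparison is also explicit: "The primary analysis will compare the EaseVR group against the VR sham group".

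Section 6.8.1 handles NPRS differently. It says "we will plan to plot NPRS score vs. time for every patient over the 8-week treatment period" and converts each curve to NPRS-%AUC, on which a score of 10 throughout equals 100%. Each patient then contributes one value, "forming a distribution of measures in each of the two groups", and the sentence ends: "we will use an unpaired t-test to compare the mean NPRS-%AUC for patients before and after the intervention".

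Three other sentences in section 6.8.1 might have covered the primary endpoint:

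- The opening paragraph offers generic bivariate tests, to be explored, and names no endpoint.
- The percent-change sentence reads "Percent change in PSEQ-2, PCS-4, CPAQ-8, ODI, SF-12 and total opioid usage (measured in MME) will be compared between groups using ANOVA". NPRS is not in the list.
- The covariate sentence reads "Covariates in the analysis of covariance models include study site, sex, duration of pain, opioid use, and baseline outcome scores". It names no outcome.

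**The concern.** The NPRS sentence starts with two arms and ends with two time points. These are different comparisons, and only the first is the one that section 6.6 calls primary. Whichever reading is chosen, the variable tested is not the section 6.6 endpoint.

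The consequence depends on the reading. A before/after test makes no use of the sham comparison, so a fall shared by both arms would count as a positive result. The plan itself anticipates such a fall: "Because pain is expected to decrease over time". A between-arm test keeps its type I error. However, it would report something other than the declared endpoint, leave out one of the two declared windows, and usually give up power by not using baseline. Because the text supports more than one analysis, the choice of comparison, variable and window could be made after the data are seen.

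**Working it through.** **1. The two sections side by side**

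| Element | Section 6.6 | NPRS test in section 6.8.1 |
|---|---|---|
| Comparison | EaseVRx vs sham | Two groups, then before vs after |
| Variable | Percent change from screening-week mean | Absolute NPRS-%AUC |
| Baseline | Mean of 5-7 daily scores | None |
| Windows | Weeks 1-4 and weeks 1-8 | 8 weeks only |

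The AUC is built only from the treatment period, so there is no pre-treatment AUC to compare with.

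**2. The variables differ.** Take two patients with baselines of 4 and 8 who both average 4 on treatment. Both have NPRS-%AUC = 4 × 10 = 40%. Their percent changes are (4 − 4)/4 = 0% and (4 − 8)/8 = −50%.

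**3. Inputs for sizing.** The plan gives no effect size, SD, correlation or power, so it has no power figure to reproduce. It plans for 100 completers randomized 1:1, which is 50 per arm, and p < 0.05 (taken here as two-sided). Every SD, correlation and effect below is an assumption.

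**4. Literal before/after reading.** This needs a pre-treatment value that the plan does not define; I assume one on the NPRS scale. With n patients, SD σ, correlation ρ and a fall d shared by both arms, the unpaired statistic has approximate mean d/(σ√(2/n)) and variance 1 − ρ. For σ = 2, n = 50, d = 1.0, the mean is 1.0/(2 × 0.2) = 2.5. The critical value is 1.984 and the SD at ρ = 0.6 is √0.4 = 0.632. The rejection probability is P(Z > (1.984 − 2.5)/0.632) = 0.79.

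Simulated rejection rates (20,000 trials per setting, ρ = 0.6, no device effect):

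| Shared fall (points) | 50 patients | 100 pooled |
|---|---|---|
| 0 | 0.3% | 0.2% |
| 0.5 | 14% | 38% |
| 1.0 | 79% | 99% |
| 1.3 | 97% | 100% |

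- At 1.0 point and 50 patients, the formula gives 75% at ρ = 0.4 and 88% at ρ = 0.8.
- With no fall the test is very conservative, because the unpaired standard error is 1/√(1 − 0.6) = 1.58 times too large.
- For scale, the 22% fall in the uncontrolled pilots (section 5) is 0.22 × 4 = 0.88 to 0.22 × 6 = 1.32 points at baselines of 4 to 6. How much of that sham would share is unknown.

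**5. Between-arm reading.** Assumptions: 50 per arm, SD 1.6, device effect 0.8 points, baseline with underlying mean 5.5 or 6 truncated to 4-10, shared fall of 0 or 1.0 point. There were 10,000 simulated trials per setting. With no effect, the unadjusted level rejected in 4.6% to 4.9% of trials. Power:

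| Analysis | ρ = 0.4 | ρ = 0.6 | ρ = 0.8 |
|---|---|---|---|
| Unadjusted 8-week level | 72% | 75-76% | 80-82% |
| Percent change, t-test | 67-73% | 82-85% | 98% |
| Percent change, ANCOVA | 74-75% | 85% | 98% |
| Mean NPRS, ANCOVA | 76-77% | 87% | 98-99% |

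The correlations are values before truncation. In the simulated patients they are about 0.32-0.34, 0.50-0.52 and 0.72-0.73, and the baseline SD is about 1.23-1.30.

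Closed-form check:

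- **Unadjusted level at ρ = 0.8.** The variance ratio is (1.23/1.6)² = 0.591, so the SD is 1.6 × √(1 − 0.64 × 0.409) = 1.375. The statistic's mean is 0.8/(1.375 × 0.2) = 2.91, and power is P(Z > 1.984 − 2.91) = 82%. With baseline SD 1.30 it is 80%.
- **ANCOVA of mean NPRS at ρ = 0.6.** The residual SD is 1.6 × √(1 − 0.36) = 1.28. The mean is 0.8/(1.28 × 0.2) = 3.125, and power is 87%.

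**6. Does the choice change the answer?** Across simulations under similar assumptions with a 0.8-point effect, the level test and the percent-change t-test disagreed on significance in about 15% to 23% of trials.

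**The case against.** The strongest defence is that the before/after phrase is a drafting slip that section 6.6 already resolves. An unpaired test, two groups and a stated between-arm primary comparison all point one way, and the rejection rates in step 4 describe an analysis whose pre-treatment variable had to be supplied. I accept that between-arm is the likelier intent. The step 4 figures show what the literal wording would permit, and the case does not rest on them.

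Second, with complete daily scores, 8-week NPRS-%AUC is about 10 times the weeks 1-8 mean NPRS, so the mismatch with section 6.6 is partial. That is correct. What remains missing is the baseline-relative change and the weeks 1-4 window.

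Third, the generic two-sample tests or the ANCOVA covariates could be applied to the section 6.6 endpoint. They could, but nothing in the plan assigns them to it.

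Fourth, the power gain is not uniform. At ρ = 0.4 a t-test on percent change may do worse than the unadjusted level, and ANCOVA of percent change gains only 2 to 3 points. This stands, and it is one reason to prefer ANCOVA.

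Finally, this is a proof-of-concept study. It nonetheless declares a primary comparison and a significance threshold, so its primary test should be executable as written.

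**Conclusion.** The concern holds and must be fixed before unblinding. The textual finding needs no assumption: the NPRS sentence contradicts itself, and neither reading analyses percent change from baseline over weeks 1-4 and weeks 1-8.

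The size does depend on assumed SDs, correlations and effects. On the literal reading, a shared 1.0-point fall with no device effect is declared significant in 75% to 88% of trials with 50 patients. On the likelier between-arm reading there is no type I error problem. The cost is a result that is not the declared endpoint, together with a power loss against ANCOVA of mean NPRS of about 4 to 5 percentage points at correlation 0.4, 11 to 12 at 0.6 and 16 to 19 at 0.8.

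**What to change.** Replace the NPRS test sentence in section 6.8.1 with wording such as:

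> The primary analysis compares EaseVRx with sham on percent change from baseline in average daily NPRS over weeks 1-4 and over weeks 1-8, as defined in section 6.6. It uses ANCOVA with arm as factor and the 5-7 day screening mean NPRS as covariate, together with sex, pain duration and baseline opioid use. The adjusted between-arm difference and its 95% CI are reported for each window.

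Then:

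- Keep NPRS-%AUC as a supportive EaseVRx-versus-sham comparison.
- Label any before/after summary as descriptive.
- Define the study site covariate, for example as clinic, or remove it. Section 6.1 calls the trial single-center, while section 6.5 refers to clinics in the plural.
- If the sponsor prefers ANCOVA of mean NPRS, amend section 6.6 openly to match and keep both windows.

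Reconciling the two sections is essential; the choice between these two ANCOVA forms is the sponsor's. How the two windows jointly decide success is a separate gap in section 6.6 that this change neither creates nor closes.

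The cost is wording in section 6.8.1, and in section 6.6 only if the endpoint changes. No new data are needed.

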6 STUDY DESIGN

6.1 Description

This is a single-center, prospective, randomized, double-blind, placebo-controlled study of the appliedVR EaseVRx headset in subjects with chronic lower back pain. A cohort of 126 patients will be recruited from patients currently seeking care for low back pain at Geisinger. We are assuming a 20% dropout or noncompletion rate, so recruiting 126 patients should provide 100 completes. Patients with moderate to severe chronic low back pain who have largely exhausted non-pharmacological approaches to improving pain and who are currently relying primarily on pharmacotherapy for symptom relief will be recruited for the study. These patients are an ideal study population to include as few treatment options remain for these patients due to insufficient understanding of pain origin, failure of conventional pain management approaches, or unsuitability of surgical interventions. Patients will be randomized by computer 1:1 to either the VR sham or EaseVRx group. Providers and patients will be blinded in regard to whether the patient will receive EaseVRx or the VR sham.

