6.3 Recruitment

The primary and collaborating investigator(s) will identify potential subjects in the Geisinger system who are scheduled for a clinic visit to address their chronic low back pain. These patients will be pre-screened via manual chart review of their electronic health record (EHR) by the research team. Patients meeting the inclusion/exclusion criteria will be called by an IRB-approved study team member (e.g. primary and collaborating physicians, research project coordinator, research assistant) approximately one week prior to their scheduled clinic visit. After hearing a description of the study and completing a short screening assessment, eligible

patients will be asked to report their average lower back pain over the last 24 hours via a Numeric Pain Rating Scale (NPRS) score for 7 days. Each subject will choose how they want to report their daily NPRS scores and will be given the following options: phone calls, texts, or web-based entry via REDCap. They will be instructed to record their scores at the same time each day (\pm 2 hours).

At the end of the 7-day screening period, the study team will assess daily NPRS scores to determine if the subject meets the pain eligibility requirements: (1) subjects must complete at least 5 of 7 daily NPRS scores in the previous 7-day screening period and (2) the overall average NPRS score must remain between 4 and 10 (inclusive) during the screening period. Subjects who are deemed eligible will be approached by a member of the study team during their clinic visit to provide more information about the study and administer informed consent for interested patients.

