6.7 Secondary Endpoints

Secondary outcome measures include:

- Average daily minutes of VR or sham use at during weeks 1-4 and weeks 1-8.
- Number of days VR or sham used.
- Number of days that participants completed all outcome assessments.
- Patient satisfaction score (min 3 – max 12).
- Likelihood of recommending VR treatment to someone else (min 1 – 10 max).
- Number of adverse events related to the study treatment.
- Change from baseline PSEQ-2, PCS-4, CPAQ-8, SF-12 score at 4, 8, and 12 weeks.
- Change from baseline in total ODI score as well as subscale scores at 4, 8, and 12 weeks.
- Average self-reported daily amount of analgesic medication used during weeks 1-4 and weeks 1-8.
- Total milligrams of morphine equivalent doses filled from PDMP database at 3 months, 6 months, and 12 months.
- Total number of office visits, admissions, emergency room visits, and therapy sessions related to the patient's lower back pain at 3 months, 6 months, and 12 months.
- Total cost of care related to patient's lower back pain at 3 months, 6 months, and 12 months.

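### Section 6.8.1 tests percent change in five scales that section 6.7 defines as change from baseline, has no rule for a zero baseline, and leaves the opioid metric ambiguous

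*Combined protocol and SAP*

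**What the plan says.** Section 6.7 (Secondary Endpoints) lists "Change from baseline PSEQ-2, PCS-4, CPAQ-8, SF-12 score at 4, 8, and 12 weeks" and "Change from baseline in total ODI score as well as subscale scores at 4, 8, and 12 weeks". For opioids it lists "Total milligrams of morphine equivalent doses filled from PDMP database at 3 months, 6 months, and 12 months".

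Section 6.8.1 (Statistical Analysis Plan) gives the test: "Percent change in PSEQ-2, PCS-4, CPAQ-8, ODI, SF-12 and total opioid usage (measured in MME) will be compared between groups using ANOVA", with Kruskal-Wallis as the alternative. The same section adds: "Covariates in the analysis of covariance models include study site, sex, duration of pain, opioid use, and baseline outcome scores".

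Among the endpoint definitions, only the primary one in section 6.6 is a percent change: "the percent change from baseline (defined as the average of the 5-7 pain scores obtained in the week prior to enrollment/randomization". Pain has a floor at entry, because section 6.3 says "the overall average NPRS score must remain between 4 and 10 (inclusive) during the screening period".

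Section 6.1 describes the patients to be recruited as "currently relying primarily on pharmacotherapy for symptom relief". That description is not among the inclusion criteria in section 6.2.2, and no criterion there requires opioid use. Section 6.5 lists both PDMP fills and self-report as sources for analgesic use.

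**The concern.** The protocol uses change and percent change as separate terms, and nothing says which one governs the five scales. The planned test would therefore estimate something other than the endpoint in 6.7, or the choice would be left until the data are in.

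Percent change also needs a baseline above zero. Pain is protected by its entry floor; the other measures have none. The plan does not say what happens to a patient whose baseline is zero. By default such a patient has no value, and Kruskal-Wallis cannot rank a value that does not exist.

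ODI and analgesic use each carry a named secondary aim (4.2 and 4.3). The coping scales appear in the aim in 4.1, although 6.6 and 6.7 place them among the secondary endpoints. If the opioid comparison is also a percent change, the patients left without a value are those not taking opioids at the start, and a new opioid start among them would not be seen.

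**Working it through.** **The plan's own numbers.** Section 6.8.2 recruits 126, allows 20% dropout and expects 100 for analysis. 100 / (1 − 0.20) = 125, and 126 × 0.80 = 100.8, so the figure reproduces. I use 50 per arm below. The documents give no SDs, effect sizes or share of patients with a zero baseline, so all inputs in steps 4 and 5 are assumptions, with tests at two-sided 0.05.

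**1. The definitions side by side.**

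| Measure | Endpoint (6.6, 6.7) | Test (6.8.1) | Can baseline be zero? |
|---|---|---|---|
| PSEQ-2 | change | percent change | Yes: 2 items scored 0–6, total 0–12 (Attachment 6) |
| PCS-4 | change | percent change | Yes: 4 items scored 0–4, total 0–16 (Attachment 7) |
| CPAQ-8 | change | percent change | Yes on a simple sum, 0–48 (Attachment 8; no scoring key) |
| ODI | change | percent change | Cannot be confirmed: form not attached |
| SF-12 | change | percent change | Not on a raw sum: codes start at 1 (Attachment 5) |
| Opioids | total MME filled | percent change or total, depending on reading | Yes: opioid use not required (6.2.2) |
| NPRS | percent change | not in this sentence | No: entry mean at least 4 |

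**2. The metrics can disagree in direction.** A constructed PCS-4 example (lower is better), with two patients per arm:

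- Arm A, 1 to 3 and 12 to 8: mean change (2 − 4)/2 = −1.0; mean percent change (200 − 33.3)/2 = +83.3%.
- Arm B, 8 to 8 and 8 to 7: mean change (0 − 1)/2 = −0.5; mean percent change (0 − 12.5)/2 = −6.25%.

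Arm A is better on the endpoint in 6.7 and worse on the test in 6.8.1.

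**3. Zero baseline.** Percent change is 100 × (F − B)/B, with B the baseline and F the follow-up score. At B = 0 it is undefined.

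**4. Power for the scales.** 4,000 simulated trials per setting, with rounded normal scores clipped to the scale range. ANCOVA models F on arm and B. Patients with B = 0 are left out of the percent-change analyses only.

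| Scale (assumed baseline mean, SD, correlation, effect) | ANOVA, % change | Kruskal-Wallis, % change | Rank ANCOVA of % change with baseline | ANCOVA of score |
|---|---|---|---|---|
| PCS-4 (7, 4, 0.5, 2) | 46% | 68% | 72% | 79% |
| PSEQ-2 (5, 3, 0.6, 1.5) | 48% | 69% | 78% | 85% |
| CPAQ-8 (24, 8, 0.6, 4) | 52% | 71% | 82% | 87% |
| ODI, taken as 0–100 (40, 15, 0.7, 7) | 64% | 83% | 85% | 89% |

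Over all settings run, ANCOVA of the score gains about 4 points (ODI, 85.2 to 89.3%) to 11 points (PCS-4 at mean 5, 66.7 to 77.6%) over the baseline-adjusted rank analysis of percent change. Simulated zero baselines were 13/5/2% for PCS-4 at means 5/7/9, 7/1% for PSEQ-2 at means 5/7, 0.2% for CPAQ-8 and 0.4% for ODI. These shares partly reflect the clipping at zero.

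**5. MME, if percent change applies.** With a share q of patients having no baseline fills, 100 × (1 − q) of 100 have a value: 90/70/50/30 at q = 10/30/50/70%. Assumed for power: user baseline lognormal(7, 1), log-SD of follow-up 0.6, new starters lognormal(6, 1). Power at those four values of q:

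| Setting | Kruskal-Wallis on % change, users only | Rank ANCOVA of total MME, all patients |
|---|---|---|
| User MME × 0.7; starts 5% in both arms | 76/65/51/32% | 70/51/28/9% |
| User MME × 0.7; starts 15% vs 5% | 78/66/52/32% | 74/65/53/42% |
| No effect in users; starts 20% vs 5% | about 5% | 6/9/21/43% |

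In the first setting, a rank test stratified by baseline use, on baseline-adjusted ranks of total MME, gives about 70/56/40/22%. Without baseline adjustment it gives about 29/23/17/10%. Ranking users on F/B is no alternative to percent change: F/B = 1 + (percent change)/100, so the ranks are the same. Repeat runs of the main settings agreed to within about 3 points.

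**The case against.** **The opioid sentence can be read another way.** It may compare percent change in the five scales and, separately, total opioid usage. That reading agrees with 6.7, and the lack of a baseline PDMP window fits it. This stands. A reader might infer that the plan takes MME as a percent change; the documents do not settle that. On the other reading, the MME mismatch and its zero-baseline problem fall away, and the mismatch for the five scales remains.

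**Silence is not exclusion.** A reader might infer that the plan removes patients with a zero baseline. It does not say so; having no value is only the default when no rule is given. Section 6.8.1 also has a general sentence on t-tests and Mann-Whitney tests that could cover change scores. It names no endpoint, however, while the percent-change sentence names these scales.

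**Zero scale scores may be rare.** A PCS-4 total of 0 needs the lowest answer on all four items, in patients whose mean pain is at least 4. This stands: the true share is unknown and may be small. For CPAQ-8, ODI and SF-12 the point is essentially the mismatch with 6.7.

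**The large power gaps are not the fair comparison.** Plain ANOVA ignores baseline, although baseline scores are listed as covariates. This also stands, so the relevant gain is 4 to 11 points. The covariate sentence does not cure the problem, because it sets neither the outcome metric nor a zero rule.

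**The stakes are limited.** These are secondary endpoints in a trial that the abstract calls proof-of-concept. A reader might extend the zero-baseline problem to the primary endpoint; the entry floor of 4 rules that out.

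**Conclusion.** The mismatch for PSEQ-2, PCS-4, CPAQ-8, ODI and SF-12 is in the text and needs no assumption: 6.7 defines change and 6.8.1 tests percent change. The missing zero rule is demonstrable for PSEQ-2 and PCS-4, where the attached forms allow a total of 0. The opioid part is conditional on one reading of an ambiguous sentence, and what is established there is the ambiguity.

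This should be fixed, mainly so that the test matches the defined endpoint and every patient with data has a value. Power is a minor reason for the scales. It is no general reason for MME, where the change can cost power if the effect is confined to existing users and opioid starts are equal. All power figures and zero-baseline shares rest on assumed inputs, and the conclusion does not depend on them.

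**What to change.** **Scales.** In 6.8.1, delete percent change for the five scales. Analyse each score (or its change) at 4, 8 and 12 weeks by ANCOVA with its own baseline as covariate, as the covariate sentence already contemplates. A zero baseline then needs no special rule.

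**MME.** Name the source. State that the comparison is of total MME filled per period, as 6.7 defines it, in all patients, by a method that allows zeros and adjusts for baseline MME over a stated PDMP look-back window before randomisation. Add a supportive analysis in baseline users. A rank test stratified by baseline use is an option, provided that users are ranked on baseline-adjusted total MME. Report by arm how many patients had no baseline fills and how many of those later filled an opioid.

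**Cost.** Analysis wording, plus definition and extraction of a baseline PDMP window; no new patient contact. The named downside is the possible loss of MME power shown in step 5, which the supportive analysis in users partly addresses.

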6.2 Study Population

6.2.1 Approximate Number of Subjects

Approximately 126 Geisinger subjects will participate in this study (63 in each study arm).

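### The secondary scales have repeated visits but no longitudinal model or missing-visit rule; as most naturally read, the plan gives at least 15 separate tests, each on attenders only

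*Combined protocol and SAP*

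**What the plan says.** The analysis of the scales is one sentence in section 6.8.1: "Percent change in PSEQ-2, PCS-4, CPAQ-8, ODI, SF-12 and total opioid usage (measured in MME) will be compared between groups using ANOVA". The sentence allows Kruskal-Wallis instead where that fits better. It names no visit.

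The visits come from section 6.7, which lists "Change from baseline PSEQ-2, PCS-4, CPAQ-8, SF-12 score at 4, 8, and 12 weeks" and "Change from baseline in total ODI score as well as subscale scores at 4, 8, and 12 weeks". The opioid measure in the same analysis sentence has its own times: "Total milligrams of morphine equivalent doses filled from PDMP database at 3 months, 6 months, and 12 months".

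Section 6.8 applies one threshold to every analysis, "with p-values of <0.05 considered statistically significant". Section 6.8.1 ends with "Covariates in the analysis of covariance models include study site, sex, duration of pain, opioid use, and baseline outcome scores", without saying which outcomes those models serve.

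The documents give no repeated-measures model, imputation, missing-visit rule, key visit or testing order for the scales. The one device for irregular data, interpolation between measurements, is confined to the daily NPRS scores. Sections 6.1 and 6.8.2 expect about 100 analysable patients from 126 recruited.

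**The concern.** Three time points per endpoint, paired with a test that takes one outcome per patient, leave the repeated visits unaddressed. Kruskal-Wallis cannot model them at all. A comparison of change at a visit needs both the baseline score and that visit's score, so with no imputation a patient who misses week 12 leaves the week-12 comparison, and that patient's week-4 and week-8 scores do not inform it.

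Two things are at stake. First, if patients who are not improving stop answering, and do so more in one arm, the late-visit comparison is between selected groups. Second, with every scale and visit judged at the same threshold and none marked as the key one, a chance finding on function, coping or quality of life can be reported as significant. The abstract says the trial prepares for a larger efficacy trial, so an inflated or chance effect could carry into that design.

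**Working it through.** **The plan's own figure.** 100/(1 − 0.20) = 125, and 126 × 0.80 = 100.8. The recruitment figure of 126 (63 per arm) reproduces. At that loss, 126 × 0.20 ≈ 25 randomised patients could be absent from a late-visit comparison.

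**Number of tests.** 5 scales × 3 visits = 15. This is a floor: ODI subscales add an unstated number, and the opioid measure at three times would make 18.

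**Chance of at least one false positive** (each test two-sided at 0.05, no true effects; the documents do not state sidedness):
- Independent tests: 1 − 0.95^15 = 54%. For 18 tests: 1 − 0.95^18 = 60%.
- Correlated tests, by simulation of 15 normal test statistics. The correlations are assumptions. Between-scale 0.2 and between-visit 0.5 gives 47%; 0.5 and 0.5 gives 41%; 0.5 and 0.7 gives 36%. Stronger correlations (0.7 and 0.8) give 27%.
- Expected number of false positives, whatever the correlation: 15 × 0.05 = 0.75.
- One named visit per scale (5 tests): 18–22% over between-scale correlations 0.2–0.5, and 1 − 0.95^5 = 23% if independent.

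**Effect of dropout on the week-12 estimate.** All of these inputs are assumed except the 20% loss:
- True week-12 effect −0.40 SD.
- Correlations: baseline with weeks 4, 8 and 12, 0.6, 0.55 and 0.5; week 4 with 8, 0.75; week 4 with 12, 0.65; week 8 with 12, 0.75.
- Everyone is seen at week 4. The chance of loss afterwards rises with a poorer week-4 change on a logistic scale, with the slope shown.
- The outcome is absolute change, not the percent change in section 6.8.1.

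| Slope in EaseVRx / sham (loss per arm) | Change score | Per-visit ANCOVA | Likelihood model |
|---|---|---|---|
| 1.5 / 0 (20%) | −0.53 | −0.485 | −0.40 |
| 0.5 / 0 (20%) | −0.453 | −0.434 | −0.40 |
| 1.5 / 0.75 (20%) | −0.454 | −0.435 | −0.40 |
| 1.5 / 0 (10%) | −0.47 | −0.445 | −0.40 |
| 1.5 / 1.5 (20%) | −0.40 | −0.40 | −0.40 |

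Relative excess for change scores: 0.53/0.40 = 1.33 down to 0.453/0.40 = 1.13, so 13–33% too large. For ANCOVA: 0.485/0.40 = 1.21 down to 0.434/0.40 = 1.09, so 9–21% too large. With the same rule in both arms there is no inflation. If the loss rate is then left free to differ, sham loses slightly more patients and the change-score estimate is about −0.38, marginally too small.

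**Precision at week 12.** Patients left per arm: 63 × 0.8 = 50.4.
- Change score: √(2(1 − 0.5)) × √(2/50.4) = 0.199.
- ANCOVA: √(1 − 0.5²) × √(2/50.4) = 0.173.
- Repeated-measures model, simulated: 0.168–0.171.

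Of a total gain of about 0.03, 0.199 − 0.173 = 0.026 comes from baseline adjustment alone.

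**The case against.** The strongest reply is that the plan writes neither separate tests by visit nor the exclusion of patients who miss one. That is correct: both are inferred by joining sections 6.7 and 6.8.1. A reader might take them as stated procedure, but the documents support only the weaker statement that this is the natural reading and that nothing written contradicts it.

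The covariate sentence is also a fair point. Section 6.8.1 already lists baseline scores for ANCOVA models. If those models cover the scales, nearly all of the precision gain is already planned, so a reader should not credit it to the repeated-measures model. The sentence does not remove the rest: a per-visit ANCOVA still omits patients missing the visit and still leaves 15 tests.

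A reader might infer that the week-12 effects will be a third too large. The documents do not support that. It is the top of a range that needs response-related loss to be stronger in EaseVRx than in sham, and nothing in the plan says it will be. Section 6.8.2 also regards 20% as above the rate it expects. The model's lack of bias follows from how dropout was generated, from observed week-4 data.

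A reader might also infer that one isolated p<0.05 would count as success. The plan sets no such rule, and the hypotheses in sections 4.1 and 4.2 cover all three time points. This is a proof-of-concept trial, in which strict error control over secondary scales is partly a matter of preference. What remains is that section 4.1 puts coping skills in Primary Aim 1, section 4.2 hypothesises a significant ODI benefit, and section 6.8 exempts nothing from the threshold.

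**Conclusion.** The concern holds as a weakness of method in the natural reading of the plan. The plan should be changed, but the weakness does not invalidate the trial. The plan collects three follow-up scores per scale and names only tests that use one at a time, with no rule for missed visits.

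The possible bias ranges from no inflation, when dropout works alike in the arms, to the percentages derived above when it does not. A likelihood model avoids it only if dropout depends on data already observed. The false-positive range rests on assumed correlations between scales and visits, and 54% is the figure under independence, not an expectation.

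Sections 6.7 and 6.8.1 also disagree on the outcome: change in one, percent change in the other. Percent change is undefined for a baseline score of 0, which the PSEQ-2 and PCS-4 response scales in Attachments 6 and 7 allow.

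**What to change.** In section 6.8.1, replace the ANOVA or Kruskal-Wallis comparison of percent change in the five scales with one repeated-measures model per scale:
- Outcome: absolute change at weeks 4, 8 and 12.
- Fixed effects: arm, visit, arm-by-visit, baseline score and baseline-by-visit, plus the other applicable covariates that the section already lists. Study site is constant in a single-center trial and drops out.
- Unstructured covariance.
- All randomised patients with any follow-up score.

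Name one key visit per scale in advance, for example week 8 as the end of treatment. Report the other visits and the ODI subscales as estimates with 95% CIs, labelled exploratory.

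A key visit alone still leaves 18–22% across the five scales under the assumed correlations. If the sponsor wants control across scales, a fixed testing order or Holm's procedure would give it. Any ranking is the sponsor's choice and should respect section 4.1, which places the coping scales in Primary Aim 1.

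The opioid measure has different time points and a different source, so its analysis should be stated separately.

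The cost is SAP wording and standard code in the software already named, with no new data or patients. The downside is small: fewer results can be called significant, and weeks 4 and 12 become supportive although the hypotheses in section 4 name them.
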